8.0 Study Randomization

8.1 Randomization Process

The lead statistician will create a randomization schedule for each of the two sites, amounting to 150% of expected enrollment at each site. The excess randomization codes will be used in the event that a site will have to enroll extra participants due to unexpectedly slow enrollment at another site. The nicotine doses will be identified by letter code and only Administrative Core personnel with no participant contact will have the link between the statistician's letter code and dose assignments. There will be no blinding of e-cigarette conditions. The Administrative Core will maintain the randomization schedule and the link between the alphabetic code and treatment assignment securely. A second sealed copy will be secured in a separate building to protect against loss related to fire or other unforeseen events.

The University of Vermont will be responsible for removing all identifying information from cigarettes received from the Research Triangle Institute (RTI), labeling each carton with a blind code, assigning product using this blind code based on the randomization schedule being provided by the UVM Biostatistics Core, and shipping cigarettes and e-cigarettes to each site as needed based on recruitment. Each site will be responsible for tracking product received and distributed to participants, collecting unused product from participants, and returning unused cigarettes and e-cigarettes to UVM. The participants, investigators and study staff will not have

knowledge of which product is given to a participant or whether different participants received the same or different product.

8.2 Study Product Administration

During the experimental period, participants will be provided with a 14-day supply of research cigarettes equivalent to 150% of their daily smoking rate. Those in the e-cigarette conditions will also be provided with a 14-day supply of e-cigarettes equivalent to their daily smoking rate. This rate will be calculated at Baseline 2 and will be an average daily smoking rate based on the IVR data that reports on the usage for the first seven days following the day of the first baseline visit. This will ensure adequate availability of cigarettes in the numerous locations participants may typically keep a supply (home, work, vehicle, etc.) as well as avoid expending the entire supply if they miss a scheduled visit. Participants will be instructed to use the research cigarettes for 12 weeks, at which point they are to discontinue product use.

If there is prior knowledge a participant will be missing a visit (i.e. planned vacation, laboratory closure, etc.), then the participant will be provided with an adequate supply of cigarettes to make up for the missed visit(s). The participant will be given a 21-day supply if one visit is going to be missed and a 28-day supply if two visits are going to be missed.

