The goal of the proposed trial is to experimentally model whether increasing the availability and appeal of an alternative, non-combusted source of nicotine (e-cigarettes) enhances the effects of reduced-nicotine cigarettes in smokers with ADs. Daily smokers with current ADs, recruited at University of Vermont and Brown University, will be randomized to one of the following four conditions: (1) normal nicotine content cigarettes (NNCCs) alone, serving as the control condition, (2) VLNCCs alone, (3) VLNCCs + nicotine e-cigarettes in only tobacco flavors (TF e-cigs), or (4) VLNCCs + nicotine e-cigarettes in preferred flavors (PF e-cigs). Participants will be asked to use only their assigned study products for 16 weeks. Outcome measures include total CPD, cigarette demand assessed by behavioral economics-based purchase tasks, craving, withdrawal, psychiatric symptoms, breath carbon monoxide (CO) and biomarkers of tobacco toxicant exposure. In Week 17, participants will receive incentives to abstain from cigarettes during a three-hour laboratory test session and we will assess the effects of study conditions on cigarette demand, craving and withdrawal.

This research will address the following specific aims: Aim 1 (Primary): Compare the effects of (1) NNCCs alone, (2) VLNCCs alone, (3) VLNCCs + TF e-cigs and = (4) VLNCCs + PF e-cigs on total CPD in smokers with ADs. We hypothesize that at Week 16, total CPD will be reduced in a linear, graded manner (condition 4 > 3 > 2 > 1), with the largest reduction in the VLNCC + PF e-cig condition. Aim 2 (Secondary): Compare the effects of the four study conditions on cigarette demand, psychiatric symptoms, and biomarkers of smoke and tobacco toxicant exposure (CO, NNAL, PAHs) in smokers with ADs. We hypothesize that at Week 16, cigarette demand, CO, and toxicant biomarkers will have decreased in a linear, graded manner, with the largest reduction in the VLNCC + PF e-cig condition. We will characterize effects on psychiatric symptoms but are not testing specific hypotheses on these symptoms. Aim 3 (Exploratory): To explore the effects of the four study conditions on cigarette demand, craving, and withdrawal in smokers with ADs during the abstinence assessment period.

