3.7. Summary

Although smoking rates have declined in the overall US population, there has been little to no decline among people with ADs. A nicotine reduction strategy for combustible tobacco combined with e-cigarette availability may have complementary effects on smoking reductions and consequent tobacco-related health effects in this vulnerable population. This research is highly significant because it will model how the availability of e-cigs, a non-combusted nicotine product that is rapidly increasing in use among US smokers, impacts the effectiveness of a reduced-nicotine policy for cigarettes in this vulnerable population. It is responsive to the goals of the FDA in that the study conditions are designed to model real-world scenarios of possible harm reduction policies in a population that is vulnerable to smoking persistence.

4. Project Study Methods

This study will use a four-condition, parallel-groups research design. After a baseline period in which daily smoking rate and other baseline assessments are completed, participants will be randomly assigned to one of the following four conditions for a 16-week experimental period: (1) normal nicotine content cigarettes (NNCCs, 15.8 mg/g) alone, which serves as the control condition; (2) very low nicotine content cigarettes (VLNCCs, 0.4 mg/g) alone; (3) VLNCCs + tobacco-flavored nicotinized e-cigs (TF e-cig, 4.8 - 5.0% nicotine by weight, NBW, if they choose to use the Vuse or JULL devise, respectively); or (4) VLNCCs + preferred-flavor nicotinized e-cigarette (PF e-cig).

5. Study Screening Procedures

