Participants will be seen weekly throughout the 16-week experimental period. Weeks 4, 8, 12, 16 and the abstinence visit will take approximately 2-4 hours each. All other sessions will last approximately 2 hours. If a participant has a positive urine or saliva toxicology test or is visibly intoxicated as determined by slurred speech, swaying, or stumbling, the session will be rescheduled until a negative test result is obtained and intoxication is not present. As a part of each experimental visit, participants will be asked to come to UHC for a product exchange. All participants must pass a COVID19 screening before entering the building. Participants will be instructed to contact the RA at the office when they get to the clinic to ensure that there is enough space in the smoking chambers to house all participants while abiding by safety guidelines as detailed on page 14 of the protocol. All participants must pass a COVID19 screening before entering the building. When invited into the lab, the participant will be shown to a smoking chamber and will be instructed to place their bag of product outside of the chamber. The participant will wait here while the RA processes and returns product through the randomization database. Then the RA will dispense new product and bring the bag back to the participant's smoking chamber and leave it on the ground in front of the chamber. When the RA deems it safe for the participant to exit the chamber, the RA will instruct the participant that they can leave. The RA will instruct the participant to observe social distancing measures during this exchange, providing clarification if necessary. At the end of each experimental session, the researcher will complete the End of Visit Evaluation Form, which will be filed in the participant's binder. This will allow the researcher to make note of any problems encountered during the visit and to assess the truthfulness of the participant in regards to self-report of tobacco use and compliance to study procedures.

Visit scheduling requirements for experimental period:

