Participants will continue to use the IVR system on a daily basis throughout the experimental period to record the number of study cigarettes smoked per day, measurement of e-cig use and use of non-study cigarettes or other tobacco products. Measurement of e-cig use will be collected by asking two questions: how many daily e-cigarette episodes occurred, where one episode consists of around 10-15 puffs or up to approximately 10 minutes, and what proportion of pods and/or cartridges were used per day. Participants will also be asked to log how many flavors of e-cigs they used per day. During the first week after Baseline 1, the IVR system will collect information about mood and withdrawal symptoms.

7.5. Variable Incentive Program:

An incentive program has been developed with the goal of improving attendance at scheduled assessment sessions, compliance with using only study-provided tobacco products, and encouraging honest self-reports regarding all nicotine/tobacco use.

Briefly, participants will receive a total of seven tickets for each weekly visit they attend after randomization (Visits 03-18, weeks 1-16). In total, participants could earn 112 valid tickets across the 16 visits. Participants will be instructed that these tickets correspond to attendance (one ticket), honest reporting (one ticket), compliance in bringing back used and unused pods/cartridges (two tickets) and adherence to using only the assigned study product (three tickets). Participants who do not bring back all of their unused study product and used packaging will be told that they may not be eligible to earn the two compliance tickets. Participants will be further instructed that all of the tickets that they receive "could" be eligible for entry into a monthly drawing for prizes, but that only tickets that are "validated" will be eligible for prizes.

Since it is prohibitively expensive to test urine samples each week for each participant and because it is currently not feasible to detect with reasonable precision non-compliance

based on biomarkers in the two higher nicotine group, we plan to only validate the attendance tickets. Hence, each participant who attends their regularly scheduled weekly session will have a total of seven validated tickets entered into the monthly drawing.

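### Section 8.2 tells participants to stop product after 12 weeks, while the rest of the plan runs product use to Week 16: a probable drafting error that should be corrected

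*Combined protocol and SAP*

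**What the plan says.** Section 8.2 (Study Product Administration) gives the instruction at issue: "Participants will be instructed to use the research cigarettes for 12 weeks, at which point they are to discontinue product use". The same paragraph opens with the supply rule: "During the experimental period, participants will be provided with a 14-day supply of research cigarettes". That rule gives no number of weeks.

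Section 1 gives the duration directly: "Participants will be asked to use only their assigned study products for 16 weeks". It also places the primary hypothesis at the end of that period: "We hypothesize that at Week 16, total CPD will be reduced in a linear, graded manner".

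Section 4 says that "participants will be randomly assigned to one of the following four conditions for a 16-week experimental period", and Section 7.1 repeats the length: "Participants will be seen weekly throughout the 16-week experimental period". Section 7.1 also attaches product handling to every visit: "As a part of each experimental visit, participants will be asked to come to UHC for a product exchange". Section 7.6 has staff counsel participants on study product use at each visit from Baseline 2 through Week 16. Section 8.4 hands unused product back to participants in Weeks 1-15 and collects what remains at Week 16.

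**The concern.** The sentence is a current operating instruction about what participants are to be told, in the section that governs product administration. It is not background text. It gives a duration four weeks shorter than Section 1, and no other passage explains the difference, for example as a planned washout.

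Week 16 carries much of the inference. It is the time point of the Aim 1 hypothesis (Section 1), the basis of the sample size (Section 9.2), and one of the two post-randomization urine and saliva collections (Section 7.3). It also supplies the end-of-study data to which Section 9.1 applies the linear-trend comparison.

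If participants stopped study cigarettes at Week 12, two other rules would make the problem harder to see:

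- Section 8.3 asks participants to refrain from non-study cigarettes, so they would have no sanctioned cigarette in Weeks 13-16.
- Section 9.1 counts study and non-study cigarettes together, by assigned condition. Those weeks would enter the primary analysis as ordinary data, not as missing data.

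**Working it through.** **1. The plan's own figure.** Section 9.2 gives 53 per condition, sized on Week 16, for effect size 0.60, 80% power, two-sided alpha 0.05 and 15% loss.

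- A two-sample t-test needs 44.6, rounded up to 45 evaluable per condition (power with 45 per condition: 0.804).
- Allowing for loss: 45 / (1 - 0.15) = 52.9, rounded up to 53.

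The figure reproduces. Product duration is not an input, so correcting 12 to 16 leaves it at 53.

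**2. Which duration do the totals support?**

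| Quantity | Stated | With 16 weeks | With 12 weeks |
|---|---|---|---|
| Tickets (Section 7.5), 7 per weekly visit | 112 | 7 x 16 = 112 | 7 x 12 = 84 |
| Total compensation (Section 7.9) | $2,816 | $2,816 | $2,268 |

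- 16 weeks: 2 x 50 (screening) + 18 x 100 (Baseline 1 to Week 16) + 15 x 20 (on-time bonus) + 120 (abstinence session) + 40 (30-day verification) + 306 (daily calls) + 150 (completion) = 2,816.
- 12 weeks, assuming four fewer visits, on-time bonuses and call weeks (a call week pays 7 x 1 + 10 = 17): 100 + 1,400 + 220 + 120 + 40 + (306 - 4 x 17) + 150 = 2,268.

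These totals fix the visit schedule at 16 weeks. The tickets say something about product too, because three of the seven at each visit are described as being for adherence to the assigned product.

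**3. Which rules separate 12 from 16 weeks of product use?**

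- *They do:* Section 1 (16 weeks, stated outright), Section 7.1 (new product dispensed at each experimental visit), Section 7.6 (product counseling to Week 16) and Section 8.4 (hand-back in Weeks 1-15, collection at Week 16).
- *Only indirectly:* the supply rule in Section 8.2. It refers to the experimental period, and 16 weeks has to be brought in from Sections 4 and 7.1.
- *They do not:* the daily telephone reports in Section 7.4 also record non-study cigarettes, so they would continue under either reading. The Week 16 pregnancy rule in Section 13 says the participant is no longer receiving product, which is true whether supply ended at Week 12 or Week 16.

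Among the rules that do separate the two, the Section 8.2 sentence is the only one that points to 12.

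**4. Size if the sentence is followed literally.**

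- Weeks off study cigarettes: 16 - 12 = 4, so 4/16 = 25% of the weekly means.
- Biomarker collections after randomization: Weeks 8 and 16, so 1 of 2 is affected.
- Weekly means through Week 12 and the Week 8 biomarkers are unaffected.

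If the 16-week procedures are followed, 0 weeks are affected.

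**The case against.** The strongest reply is that this is one wrong numeral whose intended value is plain. To act on it, staff would have to disregard the weekly product exchange, the counseling through Week 16 and the hand-back and collection rules. What participants hear also depends on scripts, SOPs and consent text that are not in the documents reviewed. All of this stands, and it makes actual harm unlikely. It does not make the sentence correct: it is still an operative instruction that conflicts with Section 1.

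A reader might infer more than the documents support:

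- **That a 12-week exposure was intended.** The other product rules that distinguish the two durations say otherwise. Section 3.1 describes an earlier 12-week study by the same team, and the number may have been carried over from it, but that is an inference.
- **That Section 8.2 flatly contradicts itself.** Its supply rule gives no week count, so that conflict is indirect. The direct conflict is with Section 1.
- **That all product would stop at Week 12.** The sentence names research cigarettes and then speaks of product use generally. Whether the two e-cigarette conditions would also stop e-cigarettes is unclear.
- **That power is lost.** The documents give nothing from which to estimate how far stopping would dilute the Week 16 effect.
- **That the abstinence session would fail to measure cigarettes in use.** It is not meant to: Section 7.8 has participants encouraged not to smoke for about 24 hours beforehand. At most, recent prior exposure to study cigarettes would be missing.

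**Conclusion.** The inconsistency is real and unreconciled, and very probably a drafting error. Its effect lies between nothing, if the 16-week procedures are followed (very likely), and the loss of on-product study-cigarette data for Weeks 13-16, if the sentence is followed as written. In the second case the affected data include the Week 16 time point of Aim 1 and of the sample size, and the Week 16 biomarkers. That upper end assumes that every participant is told 12 weeks and complies, which the documents cannot confirm. The correction is worth making because the instruction reaches the primary time point and costs almost nothing to repair. It is not evidence that the design or the analysis is unsound.

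**What to change.** In the Section 8.2 sentence, change 12 weeks to 16 weeks. Check participant scripts and SOPs for the same figure and correct it wherever it appears.

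Do not use the correction to add an explicit instruction that the e-cigarette conditions stop e-cigarettes at the Week 16 visit. Sections 1 and 7.8 ask only for abstinence from cigarettes or smoking around the next-day session, so such an instruction would be a new rule that could alter what that session measures.

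The cost is a one-number protocol correction and a document check. The 53 per condition, the visit schedule, the ticket and payment totals and the analysis all stay as they are.

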8.3 Guidelines for Reporting other Nicotine Product Use

Participants will be asked to refrain from use of other non-study cigarettes during the study period. If participants have to use another nicotine product, they will be told to use a non-combustible product (gum, patch, etc.). Additionally, they will be told there is not a penalty for use of non-study products, and that it is crucial for them to report any use of non-study tobacco products. Throughout the baseline and experimental periods, an Interactive Voice Response (IVR) system will be used on a daily basis to record the number of study cigarettes and non-study cigarettes used the previous day. During the baseline and first experimental week, participants will also answer daily IVR questions about their mood. Participants will be seen weekly for assessments. Brief standardized review sessions focusing on compliance with the study cigarettes and other study procedures will be provided at each visit.

8.4 Product Accountability:

Participants will be required to keep track of all the products provided to them. Therefore, they will be instructed to return all unused products and empty cigarette packs e-liquid pods/cartridges to the laboratory each week. Research staff will complete the 'Product Accountability Log' as they process participants' product. Any discrepancies in the product dispensed versus product returned will be discussed and recorded in the log. Research staff will weigh all opened e-cigarette pods/ cartridges that the participant returns at all visits to determine how much e-liquid was used since the participant was last seen. Empty cigarette packs and e-liquid pods/cartridges will not be saved. Unused cigarette packs and e-liquid pods/cartridges will be re-distributed to the participants during Weeks 1-15. During Week 16, remaining unused cigarettes and e-cigarette pods/cartridges returned by the participants will be collected by the research staff.

Participants who report running out of cigarettes or e-liquid pods/cartridges prior to a scheduled weekly visit will be allowed to come in for an unscheduled visit to obtain more research cigarettes. To determine whether a rate change for cigarettes is necessary, we will look at the past two CO levels as compared to the Baseline 2 CO. If the CO trend is consistent with the self-report of smoking all of the allotted cigarettes then a rate increase will be granted. The participant will then receive cigarettes at a rate of 175% of their daily smoking rate. The maximum increase is 200% of their daily smoking rate. To determine whether a rate change for e-cigarettes is necessary, we will monitor the amount of e-cigarette use the participant is reporting and showing through product return along with any unscheduled visits. The investigator may grant an e-cigarette rate increase in increments of 25%. The maximum increase for e-cigarettes will be 200% of their baseline weekly e-cigarette dispensation rate.

If participants lose more than two packs of cigarettes and/or pods/cartridges and require an unscheduled visit to the laboratory to supplement their supply, they will be told the next time they lose more than two packs they will have to wait until their next scheduled appointment to receive more cigarettes.

9. Study 3 Statistical Methods and Sample Size

9.1 Statistical Methods

Continuous outcomes will be summarized by mean, standard deviation, median and range. Categorical outcomes will be summarized by frequencies and percentages. Skewed continuous outcomes will be log- or square-root transformed as appropriate. Variables measured at each baseline visit will be averaged and the average will be used as the baseline measurement. As we expect conditions to be balanced on important baseline characteristics due to randomization, our primary analysis for all endpoints will not be adjusted for potential confounders. However, a secondary analysis will be completed for all outcomes adjusting for demographic characteristics (e.g., age), that we have found to be important in prior studies. Potential moderators (e.g., SSRI vs. non-SSRI antidepressant, depression vs. anxiety disorders, BMI above or below 30) will be explored by adding that term and the moderator-by-condition term to the model. We will examine age group and gender as potential moderators in a similar fashion.

Participants will be randomized in equal probability to one of the four conditions, with randomization stratified by site and menthol cigarette status. All analyses will follow the intent-to-treat principle (i.e. subjects will be analyzed according to condition assignment, regardless of compliance). The Primary Aim will examine the effects of condition on total CPD (study product and non-study product). CPD will be analyzed by week (mean over all days in a seven-day period) using a mixed model to account for repeated measures from the same individual.

Models will include baseline CPD as a covariate. Using a mixed model also allows us to include the effect of study site as a random effect. Additional analyses conducted using data collected at the end of the study will use orthogonal comparisons to test for a linear trend in the decrease in CPD, such that VLNCC + PF e-cig > VLNCC + TO e-cig > VLNCC > NNCC, with

the largest reduction in the VLNCC + PF e-cig condition. As we expect that differences among conditions for some of the outcomes may not follow a linear pattern, we will use related planned comparisons to test for threshold effects, specifically contrasting the NNCC condition to all three VLNCC conditions, and NNCC to the two VLNCC + e-cigarette conditions.. Analysis of cigarette demand, smoke exposure and tobacco carcinogens (Aim 2) as well as additional outcomes, including subjective effects, will be analyzed in a similar manner. Because Exploratory Aim 3 is based on abstinence-induced effects and will be examined using data collected at a single visit at Week 17, analysis will be based on an analysis of co-variance model. In addition to the effect of condition, we will include important covariates noted above. Exploratory analyses will also be conducted combining data collected from three of the vulnerable populations (disadvantaged women of childbearing age, opioid dependent individuals, individuals with AD) to explore potential differences in effects of study condition across these populations. This will be done with the addition of the effects of population and population-by-condition terms to the models described above. Study staff will make every effort to minimize missing data, and results of our ongoing trial suggest that this will be minimal. We will examine the missing data pattern, and if it is missing at random, will use all data available, without imputation.

permutation tests.¹²¹

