The following assessments will be administered as an interview and will be entered into REDCap by the interviewer at the end of the visit:

- 1) Concomitant Medications
- 2) Medical Event Form, if applicable
- 3) Health Changes Questionnaire
- 4) Time Since Last Cigarette Questionnaire

The following assessments will be completed by the participant directly in REDCap:

- 1) BDI
- 2) OASIS
- 3) COVID19 Symptom Questionnaire
- 4) Respiratory Symptom Questionnaire
- 5) MNWS
- 6) QSU (usual brand)
- 7) QSU (study cigarette)
- 8) Vaping Craving Questionnaire
- 9) CES (usual brand)
- 10) CES (study cigarette)
- 11) Vaping Evaluation Scale

- 12) PANAS
- 13) Cigarette Purchase Task - Usual Brand Cigarette Version (weeks 4, 8, 12 and 16 only)
- 14) Cigarette Purchase Task – Study Cigarette Version (weeks 4, 8, 12 and 16 only)
- 15) Cross-price Elasticity Task¹⁰⁹- e-cigarettes and combustible cigarettes (weeks 4, 8, 12 and 16 only) (for e-cigarette experimental conditions only)
- 16) Penn State Electronic Cigarette Dependence Index (weeks 8 and 16 only)
- 17) Respiratory Health Questionnaire (weeks 8 and 16 only)
- 18) FTND (weeks 8 and 16 only)
- 19) Perceived Health Risks Questionnaire (weeks 8 and 16 only)
- 20) Smoking Stages of Change Algorithm and Contemplation Ladder (weeks 8 and 16 only)
- 21) WISDM – Brief Scale
- 22) Snaith-Hamilton Pleasure Scale (SHAPS)
- 23) Drug Use Questionnaire – 1 month version (weeks 8 and 16 only)
- 24) Perceived Stress Scale (weeks 8 and 16 only)
- 25) Alcohol Use Questionnaire – 1 month version (weeks 8 and 16 only)
- 26) E-cigarette flavor rating questionnaire (weeks 4, 8, 12 and 16 only)

In the event that the REDCap website is not functioning, the assessments will be administered aloud and participant answers will be recorded securely. The interviewer will enter the data into REDCap when it resumes functioning properly. This information should be recorded in the 'End of Visit Evaluation Form'.

Biological Samples to be collected:

- 1) First void urine sample (Weeks 8 and 16 only)
- 2) Saliva sample (Weeks 8 and 16 only)

7.4. Interactive Voice Response System:

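### Section 9.1 names baseline CPD as the only baseline covariate and does not say that each other outcome takes its own baseline, or from which visit

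*Combined protocol and SAP*

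**What the plan says.** Section 9.1 makes these statements on baselines and covariates:

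- Definition of baseline: "Variables measured at each baseline visit will be averaged and the average will be used as the baseline measurement".
- Adjustment: "our primary analysis for all endpoints will not be adjusted for potential confounders". A secondary analysis adds demographic covariates for all outcomes, and moderators are explored by adding terms.
- The CPD model: "Models will include baseline CPD as a covariate". Site may enter as a random effect.
- Demand, smoke exposure, carcinogens (Aim 2) and additional outcomes: these "will be analyzed in a similar manner".
- Aim 3: an analysis of covariance using covariates mentioned earlier in the section. Own baselines are not among them.

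The assessment schedules (sections 5.4, 6.2, 6.4 and 7.3.A) show which pre-product values exist:

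| Outcome | Baseline source |
|---|---|
| Breath CO, BDI, OASIS, WISDM | Baseline 1 and Baseline 2 (also screening) |
| Usual-brand purchase task, QSU, CES | Baseline 1 and Baseline 2 |
| FTND | Screening only |
| Urine biomarkers (NNAL, PAHs) | Baseline 2 only |
| Study-cigarette purchase task, QSU, CES | None; first measured after randomization |
| Contemplation Ladder | None: "Smoking Stages of Change Algorithm and Contemplation Ladder (weeks 8 and 16 only" |

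Section 6.3 has participants in the e-cigarette conditions told their condition and given pods before the Baseline 2 visit. Section 8.1 says that these conditions are not blinded.

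**The concern.** A covariate sentence that names one variable, followed by an instruction to treat everything else similarly, leaves the covariate for the other outcomes undetermined. The possible choices give different estimates and p-values from the same data, and nothing fixes the choice before the data are seen. Precision matters most where expected effects are small. The trial is sized for an effect of 0.60, while Table 2 in section 9.2 lists 0.33 for CO (Aim 2) and 0.42 for FTND. FTND is not in Aim 2. It falls under the additional outcomes of section 9.1 and is a measure of dependence, and section 17 lists dependence severity as a primary endpoint.

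A second question is which visit supplies the baseline. If the average includes a value taken after open-label allocation is known, the covariate is not strictly pre-treatment in two of the four arms.

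**Working it through.** **1. The plan's own figure.** Inputs from section 9.2: effect size 0.60, two-sided alpha 0.05, power 80%, 15% loss. A two-sample t-test (noncentral t) needs 45 per arm (power 0.804). Then 45 / (1 - 0.15) = 52.9, so 53 per condition. The stated figure reproduces, and it uses no baseline adjustment.

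**2. Readings of the covariate text for an outcome other than CPD.**

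| Reading | Support | Against |
|---|---|---|
| Own baseline | The CPD sentence follows the CPD model; the averaging rule defines baselines generally | Never stated; the averaging rule does not say that the value enters a model |
| Baseline CPD | Literal wording, since the sentence refers to models in the plural | Unlikely intent for a biomarker or a mood scale |
| No baseline | The primary analyses are described as unadjusted for confounders | The same section adjusts CPD for its baseline, so a baseline is evidently not counted as a confounder |

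Even under the first reading, the averaging rule covers only variables measured at each baseline visit. It gives no source for FTND, urine biomarkers or the study-cigarette measures.

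**3. Size of the precision effect.** For a single-time-point analysis at Week 16 with 45 evaluable per arm:

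- The residual variance is multiplied by 1 - r², where r is the correlation of the covariate with the Week 16 outcome.
- Noncentrality = [d / √(1 - r²)] × √(45/2), with 2 × 45 - 3 = 87 degrees of freedom and √22.5 = 4.743.
- d is from Table 2, taken to be standardized by the unadjusted SD. r is assumed.

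| r | 1 - r² | CO, d = 0.33: noncentrality, power | FTND, d = 0.42: noncentrality, power |
|---|---|---|---|
| 0 | 1.00 | 1.57, 34% | 1.99, 50% |
| 0.3 | 0.91 | 1.64, 37% | 2.09, 54% |
| 0.5 | 0.75 | 1.81, 43% | 2.30, 62% |
| 0.7 | 0.51 | 2.19, 58% | 2.79, 79% |

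The row r = 0.3 illustrates what baseline CPD might give if it were carried over literally. The rows 0.5 and 0.7 illustrate an outcome's own baseline. The effect detectable with 80% power falls from 0.60 (r = 0) to 0.52 (r = 0.5) and 0.43 (r = 0.7).

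**4. Timing of Baseline 2.** Under section 6.3, e-cigarette participants are told their condition after the seven-day monitoring period but before Baseline 2, and pods reach them one to two days before that visit. Baseline CPD comes from the seven days after Baseline 1 (section 8.2), so it is not affected. Baseline 2 CO, questionnaires, purchase task and urine are all collected after disclosure in two arms, and the averaging rule brings those values into the baseline of every outcome measured at both visits except CPD.

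**The case against.** The strongest reply is that this is a wording gap and not a planned omission. The covariate sentence sits directly after the CPD model, and treating other outcomes similarly can well mean that each takes its own baseline. That stands, and a reader who inferred that the plan deliberately leaves these outcomes unadjusted, or adjusts them all for CPD, would go further than the text allows. Nor is baseline CPD the only covariate in section 9.1: demographics, moderators and a random site effect are also named, though the demographics belong to secondary analyses and the moderators to exploratory ones.

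Several other limits also stand:

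- Omitting a baseline covariate from a randomized comparison does not bias it.
- The sample size rests on CPD and does not change.
- The gain depends on correlations that the documents do not give. Moving from r = 0.3 to r = 0.5 adds only 6 points for CO.
- Table 2 has no effect size for NNAL, PAHs, demand, BDI or OASIS, so CO is the only Aim 2 outcome that can be worked through. For psychiatric symptoms no specific hypothesis is tested.
- Not every outcome has a pre-treatment value, so a blanket own-baseline rule would fail for the study-cigarette measures.

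On Baseline 2, a reader might infer that its biomarker values already reflect vaping. The documents do not show that. They place pods, not use, before the visit, and section 6.3 describes the first trial of the device during the training session. What is documented is that values are collected after allocation is known.

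None of this supplies the missing rule, and the choice remains open until someone writes it down.

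**Conclusion.** The point holds as an ambiguity. Baseline CPD is the only baseline covariate named for the primary models, own-baseline adjustment is never stated for other outcomes, and most of the needed values are already collected. Compared with no baseline adjustment, stating it would raise pairwise power by 9 to 24 points for CO (34% to 43-58%) and by 12 to 29 points for FTND (50% to 62-79%). These figures assume r = 0.5-0.7, 45 evaluable per arm, the Table 2 effects and a single Week 16 comparison; the planned repeated-measures model could differ. The consequences of the covariate gap are precision and analyst discretion, not bias or sample size.

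The choice of visit is a separate issue. The averaged baseline includes post-disclosure values in the two e-cigarette arms. A covariate affected by knowledge of assignment could absorb part of a real effect; the documents give no basis for sizing this.

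**What to change.** In section 9.1, replace the covariate sentence with: *Each model will include the baseline value of the outcome being analysed, on the same transformed scale (baseline CPD for CPD).* Then name the source:

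- Baseline 1, not the two-visit average, for outcomes measured there (CO, usual-brand purchase task, QSU and CES, WISDM, BDI, OASIS). This accepts a small loss of precision from using one visit.
- Screening for FTND.
- Baseline 2 for urine biomarkers, acknowledging that it follows disclosure of the condition in the e-cigarette arms.
- The usual-brand baseline version as covariate for the study-cigarette purchase task, QSU and CES.

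Amend the averaging rule to match, and state the same covariates for Aim 3. Add the Contemplation Ladder to the Baseline 1 battery; participants already past that visit will have no baseline value for it.

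The cost is a few sentences in the analysis plan and one questionnaire item. No additional participants or samples are needed. The wording should be fixed before outcome data are examined by condition.
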